4.2 Exclusion Criteria

Patients who meet any of the following exclusion criteria will not be eligible to participate in the study:

1. Have participated in another clinical trial within the last year where patient received active treatment for NASH.
2. Have participated in a clinical trial for any other indication within the last 3 months or 5 half-lives of the treatment, whichever is longer.
3. Have participated in another Corcept study with miricorilant.
4. Women who are pregnant, planning to become pregnant, or are lactating.
5. Have a BMI <18 kg/m².
6. Are currently using any medications prohibited due to the potential for drug-drug interactions (DDI) with study treatments Prohibited medications (see Section 5.4.3) must be discontinued at least 5 half-lives prior to a patient receiving their first study treatment. Administration of concomitant medications (see Section 5.4) are at the discretion of the Investigator and/or the Corcept Medical Monitor.
7. Have had successful weight-loss surgery prior to Screening or are planning weight-loss surgery during the study*.

*Patients who have had Roux-en-Y gastric bypass surgery or other surgical procedures that have a fundamentally altered gastrointestinal tract may not participate regardless of success of the procedure.

8. Have any elective surgery planned during the study.
9. Have significant alcohol consumption, defined as more than 2 drink units per day (equivalent to 20 g of ethanol) in women and 3 drink units per day (equivalent to 30 g of ethanol) in men for ≥ 3 consecutive months within 1 year prior to Screening, inability to reliably quantify alcohol intake, or score a value ≥ 8 on the Alcohol Use Disorders Identification Test (AUDIT) questionnaire.
10. Use of drugs associated with NAFLD (e.g., amiodarone, methotrexate, oral or intravenous GCs, at supraphysiological doses (prednisone equivalent ≥ 5 mg/day), tamoxifen, estrogens at doses greater than those used for hormone replacement or contraception, anabolic steroids, or valproic acid) for more than 4 weeks in the 2 months prior to randomization.
11. Have been treated with obeticholic acid, ursodeoxycholic acid (Ursodiol[®] and Urso[®]), pioglitazone or high-dose vitamin E (>400 IU/day) within the 3 months prior to Screening imaging studies.
12. Have had liver transplantation or plan to have liver transplantation during the study.
13. Have type 1 diabetes.
14. Have type 2 diabetes and:
 - a. An HbA1c $\geq 9.5\%$
 - b. Have had an insulin dose adjustment >10% within 60 days prior to enrollment
 - c. Have a requirement for glucagon-like peptide analogue (unless on a stable dose ≥ 3 months prior to Screening), a requirement for sodium/glucose cotransporter 2 (SGLT2) inhibitors (unless on a stable dose ≥ 3 months prior to Screening), or 3 or more oral anti-diabetic (OAD) agents (unless the OAD is stable and HbA1c <8%)

- d. Have a history of severe hypoglycemia (symptomatic hypoglycemia requiring outside assistance to regain neurologic status)
- 15. Are currently taking a statin other than stable doses of the following: lovastatin (up to 20 mg), pravastatin, pitavastatin, simvastatin (up to 10 mg), atorvastatin (up to 20 mg), or fluvastatin (up to 20 mg). A stable dose is defined as no changes in the dose in the last 3 months prior to Screening.
- 16. Are currently on the oral antidiabetic drug nateglinide (Starlix).

Patients currently taking the medication may participate in the study if it is appropriate to discontinue the medication, and if the patient is amenable to discontinuing the medication for a wash out period of 5 half-lives prior to the baseline assessment.

- 17. Are currently using a medication such as digoxin with an increased risk for toxicity in the event of electrolyte changes.
- 18. Have weight loss of greater than 10% within the last 6 months prior to Screening.
- 19. Have abnormal screening laboratories:
 - a. AST $>5\times$ upper limit of normal (ULN)
 - b. ALT $>5\times$ ULN
 - c. Estimated glomerular filtration rate (eGFR) ≤ 60 mL/min/1.73 m²
 - d. Creatine kinase $>3\times$ ULN
- 20. Have known or suspected cirrhosis based on the opinion of the Investigator. The list below represents possible signs of suspected cirrhosis:
 - a. Physical exam findings:
 - i. Jaundice
 - b. Laboratory findings
 - i. Direct bilirubin >0.3 (except for patients who have Gilbert's syndrome; see exclusion criterion #21f)
 - ii. Platelet count $<140,000/\mu\text{L}$
 - c. Imaging:
 - i. Evidence of portal hypertension (dilated portal vein, presence of varices)
 - ii. Evidence of a nodular liver with splenomegaly
 - d. Endoscopy:
 - i. Evidence of esophageal varices
- 21. Have hepatic decompensation defined as the presence of any of the following:
 - a. Serum albumin <3.5 g/dL
 - b. International normalized ratio (INR) >1.3 (unless due to therapeutic anticoagulants)
 - c. Total bilirubin >1.3 mg/dL (except for patients who have Gilbert's syndrome; see exclusion criterion #21f)
 - d. History of esophageal or gastric variceal bleedings, ascites, or hepatic encephalopathy
- 22. Have any other chronic liver disease:
 - a. Hepatitis B as defined by presence of hepatitis B surface antigen
 - b. Hepatitis C as defined by presence of hepatitis C virus (HCV) antibody and positive HCV RNA. Documented cured HCV infection is acceptable if >3 years from Screening visit
 - c. History of current active autoimmune hepatitis

- d. History or evidence of primary biliary cholangitis
 - e. History or evidence of primary sclerosing cholangitis
 - f. History or evidence of Gilbert's syndrome if direct bilirubin is elevated (in addition to total bilirubin ≥ 2) or evidence of hemolysis contributing to elevated total bilirubin
 - g. History or evidence of Wilson's disease
 - h. History or evidence of alpha-1-antitrypsin deficiency
 - i. History or evidence of hemochromatosis
 - j. History or evidence of drug-induced liver disease, as defined on the basis of typical exposure and history
 - k. Known bile duct obstruction
 - l. Suspected or proven liver cancer
 - m. Any other type of liver disease other than NASH
23. Have a history of biliary diversion.
 24. Are seropositive for human immunodeficiency virus.
 25. Have a history of cancer within the last 3 years (in situ carcinomas, cutaneous basal cell or squamous cell cancer resolved by excision are not excluded).
 26. Have contraindications to magnetic resonance imaging (MRI).
 27. New York Heart Association class III or IV heart failure, or known left ventricular ejection fraction $< 30\%$.
 28. Uncontrolled hypertension (either treated or untreated) defined as systolic blood pressure > 160 mm Hg or a diastolic blood pressure > 100 mm Hg at Screening.
 29. Uncontrolled cardiac arrhythmia, including confirmed QT interval corrected using Fridericia's formula (QTcF) > 450 msec for males and > 470 msec for females at the Screening ECG assessment.
 30. Myocardial infarction, unstable angina, percutaneous coronary intervention, coronary artery bypass graft, or stroke within 3 months prior to Screening.
 31. Active substance abuse, including inhaled or injected drugs, within 1 year prior to Screening.
 32. Have any clinical condition or significant concurrent disease judged by the Investigator to complicate the evaluation of the study treatment.
 33. Are a family member of one of the Sponsor's employees, the Investigator, or the site staff.
 34. Are directly working on the study or are a contractor directly involved in the conduct of the trial.
 35. Have an allergic reaction or hypersensitivity to miricorilant tablets.

4.3 Screen Failures

Screen failures are defined as patients who consent to participate in the clinical study but did not meet eligibility criteria for the study and were not randomized to the study drug.

Subjects who have an exclusionary laboratory result on initial screening tests may have that assessment repeated in consultation with Corcept Medical Monitor, once within the 6-week Screening period if the Investigator believes the result was spurious or otherwise confounded. The repeat assessment must meet eligibility requirement before the subject proceeds with the Screening MRI assessment.

Individuals who do not meet the criteria for participation in this study (screen failure) because of laboratory abnormalities alone may be rescreened at the discretion of the Investigator with the approval of the Corcept Medical Monitor. Rescreened patients should be assigned a new patient number. Rescreened patients should meet all of the entry criteria outlined in Sections 4.1 and 4.2.

4.4 Early Patient Discontinuation or Withdrawal

In this study, patient “discontinuation” refers to early discontinuation of study treatment while remaining on study; that is, the patient may wish to stop treatment early but may agree to continue with study visits and/or assessments.

Early patient “withdrawal” refers either to patient withdrawal of consent to any further study participation or to an Investigator/Sponsor decision to permanently withdraw the patient and cessation of all study treatments, procedures, and assessments without further follow-up. If a patient wishes to withdraw consent to further participation in the study entirely, this should be clearly documented (1) in the patient’s medical record and signed by the Investigator and (2) in the clinical study database/electronic case report form (eCRF).

4.4.1 Early Patient Discontinuation of Study Drug

Study drug may be discontinued in the event of any of the following occurrences:

- Unacceptable toxicity.
- The Investigator decides it is in the patient’s best interest to discontinue treatment and/or participation in the study. Reasons may include but are not limited to the following:
 - The patient requires prohibited medications.
 - The patient is not compliant with protocol requirements.
- Patient becomes pregnant.

If a patient discontinues early from study drug, that patient will complete an Early Termination (ET) visit at the time of the last dose of the study drug, or soon thereafter. The Follow-Up visit will be conducted 28±5 days after the last dose of the study drug. Investigators should encourage these patients to continue with all study visits and/or assessments per the patient’s original study schedule through Week 12 (end-of-treatment). If the Follow-Up visit coincides with any other study visit, the assessments performed at these visits will be combined. If a patient is unable to continue with all study visits, they will be encouraged to complete the end-of treatment Week 12 visit at the very least, in addition to the ET and Follow-Up visits. Patients who complete at least 6 weeks of treatment and subsequently discontinue will be eligible for evaluation of liver fat content by MRI-PDFF. The date when the patient discontinues the study drug and the reason for discontinuation must be recorded on the eCRF

For guidelines about temporary interruption of study drug, see Section 5.3.

4.4.2 Early Patient Withdrawal from Study

A patient may be withdrawn early from the study for the following medical or administrative reasons:

- Withdrawal of consent.

- Noncompliance, including refusal of the study treatment and/or failure to adhere to the study requirements, as specified in protocol.
- Lost to follow-up (before a patient is determined to be lost to follow-up, reasonable efforts will be made to contact the patient and complete study termination procedures).
- Early termination of the study by the Sponsor.

The date the patient is withdrawn from the study and the primary reason for withdrawal must be recorded on the eCRF.

Patients may withdraw voluntarily from the study at any time. For patients who withdraw consent to participate in the study, every effort should be made to determine whether the withdrawal of consent was related to an AE or a specific aspect of the study. As noted above, if a patient wishes to withdraw consent to further participation in the study entirely, including follow-up, this should be clearly documented (1) in the patient's medical record and signed by the Investigator and (2) in the clinical study database (eCRF).

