9.8 Efficacy Analyses

Due to observations related to safety, the study was terminated by the sponsor prior to completion. The sample size at the time of study termination does not support formal comparisons of the treatment groups, and therefore, no efficacy analyses specified in the protocol will be performed. Descriptive statistics for efficacy endpoints will be provided as described below.

Furthermore, no patient reached their Week 12 visit, and therefore, descriptive statistics at Week 12 will not be presented. Instead, descriptive statistics will be provided for all analysis visits up to the last non-missing visit.

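### Protocol 4.4.2 lets a site withdraw a noncompliant or treatment-refusing patient with no further follow-up, while 4.4.1 keeps a noncompliant patient on study; no rule decides which applies

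*Protocol*

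**What the plan says.** Protocol 4.4 sets up two statuses. Discontinuation "refers to early discontinuation of study treatment while remaining on study". Withdrawal is either the patient's withdrawal of consent to any further participation, or a decision by the Investigator or Sponsor to "permanently withdraw the patient and cessation of all study treatments, procedures, and assessments without further follow-up".

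Section 4.4.1 gives reasons for discontinuing study drug. One is "The patient is not compliant with protocol requirements". After early discontinuation there is an ET visit and a Follow-Up visit 28±5 days after the last dose, and "Investigators should encourage these patients to continue with all study visits and/or assessments" through Week 12. Sections 7.4 and 7.5 repeat the ET and Follow-Up visits for anyone who stops drug early, whatever the reason. The ET visit includes MRI-PDFF only after at least 6 weeks of treatment.

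Section 4.4.2 gives reasons why a patient may be withdrawn from the study. Beside withdrawn consent and loss to follow-up, it names "Noncompliance, including refusal of the study treatment and/or failure to adhere to the study requirements, as specified in protocol" and "Early termination of the study by the Sponsor".

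Sections 6.4.4, 8.9 and 8.11 collect adverse events and SAEs to 28 days after the last dose, with no exception for withdrawn patients. Section 3.5 foresees follow-up after study termination but names no visit. SAP 9.8 records that "Due to observations related to safety, the study was terminated by the sponsor prior to completion" and that no patient reached Week 12.

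**The concern.** The distinction in 4.4 is sound: stopping drug is one thing, leaving the study is another. The lists beneath it undo the distinction for noncompliance, which appears in both. Section 4.4.2 adds refusal of treatment, although 4.4 itself describes the patient who wants to stop treatment and still attend as a discontinuation. The choice of status falls to the site, after randomization, and it decides whether data collection continues.

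Refusing or missing tablets can reflect poor tolerability, so the patients affected may differ by arm. If their assessments end, missing data arise that the protocol could have avoided, and SAP 7.5 does not impute missing values unless stated otherwise. On the safety side, the SAP's treatment-emergent period runs to 28 days after the last dose (SAP 7.1 and 9.9.1). A patient who stopped because of side effects could go unobserved for that period.

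**Working it through.** **1. One patient, two routes.** Take a patient who refuses further tablets after at least 6 weeks of treatment and has not withdrawn consent.

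| Item | Discontinued (4.4, 4.4.1, 7.4, 7.5) | Withdrawn (4.4, 4.4.2) |
|---|---|---|
| ET visit with MRI-PDFF | Scheduled | None |
| Remaining visits, or at least Week 12 | Encouraged (4.4.1 only) | None |
| 28±5-day Follow-Up visit | Scheduled | None |
| Adverse events to 28 days after last dose | Collected | Required by 6.4.4, 8.9 and 8.11, but all assessments have ended under 4.4 |

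No tie-break is given. Both lists are permissive, and the introductory wording in 4.4.1 speaks of stopping treatment and/or participation.

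**2. The same refusal before Week 6.** The protocol's Efficacy Evaluable (EE) set (Table 9) needs one dose and at least 6 weeks in the trial. A patient who stops drug at Week 3 and keeps attending is in the set; the same patient labelled as withdrawn is out. For liver fat the consequence is less clear, because there is no ET MRI-PDFF before 6 weeks of treatment on either route, and 4.4.1 ties MRI-PDFF after discontinuation to at least 6 weeks of treatment. Later biomarker and safety data are lost on the withdrawal route.

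**3. Scale against the sample size.** Inputs (Protocol 9.4; sidedness from 9.3): difference 35 − 10 = 25 points, SD 35, two-sided alpha 0.05, power 80%.

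- Normal approximation: 2 × (35/25)² × (1.960 + 0.842)² = 30.8, so 31 per group.
- Two-sample t-test: 31.76, so 32.
- t-test figure divided by the Wilcoxon efficiency 3/π = 0.955: 33.3, so 34. This matches the plan.
- Dropout: 34/0.90 = 37.8, so 38; 38 × 3 = 114; rounded up to 40 per group.

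The documents give no refusal or noncompliance rate. At an assumed 5–10%, 40 × 0.05 to 40 × 0.10 = 2 to 4 patients per arm. The margin over 34 is 40 − 34 = 6 per arm, or 15%. Power with equal loss in both groups:

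| Total loss | n per group | Power, t-test | Power, Wilcoxon approximation |
|---|---|---|---|
| 10% | 36 | 84.8% | 83.1% |
| 15% | 34 | 82.7% | 80.9% |
| 20% | 32 | 80.3% | 78.4% |

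Even if the assumed loss comes on top of the planned 10%, power stays near 80%.

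**4. Scale of possible bias (illustration).** Assume a true active-arm mean of −35, loss of a fraction q from that arm only, and a mean of −10 in the lost patients (placebo-like). The mean in those retained is (−35 + 10q)/(1 − q).

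- q = 0.05: −34.5/0.95 = −36.3, exaggeration 1.3 points.
- q = 0.10: −34.0/0.90 = −37.8, exaggeration 2.8 points.
- q = 0.20: −33.0/0.80 = −41.25, exaggeration 6.25 points.

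These compare with a planned difference of 25 points.

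**5. Sponsor termination.** This reason appears only in 4.4.2, so by the 4.4 definition it carries no follow-up. Sections 3.5, 7.4 and 7.5 point the other way. Post-baseline MRI-PDFF, ACTH, cortisol and aldosterone are scheduled only at Week 12 and ET (Appendix A). As no patient reached Week 12, the scheduled source of these data is the ET visit.

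**The case against.** The strongest reply is that nothing in the protocol compels loss of follow-up. Section 4.4.2 only permits withdrawal. Section 4.4 treats a patient who wants to stop tablets but keep attending as discontinued. Section 5.8 tells sites to assess, educate or manage nonadherent patients and does not call for withdrawal. The safety sections collect events to 28 days for everyone, and 8.15 follows related events and all SAEs to resolution, stability or loss to follow-up. The SAP makes no formal efficacy comparison, so the effect on inference in this trial is small.

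Much of this stands. It means that loss is possible, not required. It does not remove the conflict: a permissive rule leaves the choice to each site, and once withdrawal is chosen, 4.4 ends all assessments. The safety sections contradict that definition without overriding it.

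A reader might infer that sponsor termination deprived every patient still on drug of ET imaging and safety follow-up. The documents do not support this. Section 3.5 foresees follow-up, and 7.4 and 7.5 make no exception by reason. The SAP has follow-up windows (7.6), counts completed follow-up visits (9.2) and, for patients with complete resolution, lists the time from last dose to MRI (9.8.3.2). That does not show how much was collected, but the plan expects it. Patients treated for under 6 weeks have no ET MRI-PDFF on any reading. Termination also affects all arms together, so it concerns completeness rather than selection.

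**Conclusion.** The conflict over noncompliance and refusal of treatment is confirmed from the text. It allows avoidable, possibly arm-related loss of outcome data and lets a discretionary label decide EE membership before Week 6. It also contradicts the 28-day adverse event and SAE collection. The sponsor-termination wording is a secondary inconsistency.

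The size is modest and rests on assumptions: 2–4 patients per arm at an assumed 5–10%, little effect on power, and 1.3–2.8 points of exaggeration if 5–10% of an active arm alone were lost with placebo-like response. These figures describe the protocol's design. Under the current SAP the remaining effect is mainly on safety follow-up, the reporting of disposition and the completeness of descriptive data.

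A reader might conclude that data were in fact lost selectively, or that 7.4 and 7.5 guarantee a Week 12 visit. Neither holds. No section reports such loss, and Week 12 attendance after stopping drug appears only in 4.4.1, as encouragement.

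**What to change.** Reconcile Protocol 3.5, 4.4, 4.4.1, 4.4.2, 7.4 and 7.5 along these lines:

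- All assessments end only when the patient withdraws consent to further participation or is lost to follow-up.
- In every other case (refusal or nonadherence, Investigator or Sponsor decision, sponsor termination) the scheduled ET visit, with MRI-PDFF if at least 6 weeks treated, and the 28±5-day Follow-Up visit are still sought.
- The clause excluding further follow-up is removed from the 4.4 definition for Investigator or Sponsor decisions. This also resolves the conflict with 6.4.4, 8.9 and 8.11.

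No change is proposed to the criteria for stopping study drug. For this terminated trial, the study report should state how patients who refused treatment and those affected by sponsor termination were classified and followed.

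The cost is a few lines of wording. The visits are already in the schedule; the downside is following some patients who are off drug.

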4.5 Replacement of Patients

Not applicable.

4.6 Restrictions/Requirements/Recommendations During Study

The following apply to patients in this study (prohibited or limited-use medications are described in Section 5.4)

4.6.1 Dietary Restrictions

Patients will be asked to follow a healthy diet according to the American Heart Association guidelines (AHA 2020).

4.6.2 Alcohol

Patients will be advised to limit alcohol use (also see Section 4.2 regarding alcohol consumption).

4.6.3 Activity

Patients should engage in physical activity and are recommended to follow the Centers for Disease Control and Prevention (CDC) guidelines of 150 minutes per week of moderate-intensity aerobic activity (CDC 2020). Patients are advised to gradually increase their activity level to meet this guideline.

4.6.4 Childbearing Potential and Contraception

Miricorilant should not be administered to pregnant women due to adverse effects on fetal development (mice) or adverse pregnancy outcomes (rabbits). Men and women of childbearing potential who participate in this study must agree to use effective contraception.

All female patients of childbearing potential (including all women <50 years old, women whose surgical sterilization was performed <6 months prior to Screening, and women who have had a menstrual period in the last 12 months) will take pregnancy tests at scheduled visits

(Appendix A). The Screening pregnancy test will be a blood test. All subsequent pregnancy tests will be urine tests.

- A female patient is of childbearing potential if, in the opinion of the Investigator, she is biologically capable of having children.
- Women who are considered not of childbearing potential must meet at least 1 of the two following criteria:
 - a. Have undergone a documented hysterectomy and/or bilateral oophorectomy.
 - b. Have medically confirmed ovarian failure or have reached postmenopausal status, defined as cessation of regular menses for at least 12 consecutive months with no alternative pathological or physiological cause and have a serum follicle-stimulating hormone (FSH) level within the laboratory's reference range for ovarian failure or postmenopausal women.

Female patients of childbearing potential are required and must agree to use a highly effective method of contraception throughout the study and for at least 28 days following the last dose of study drug administration.

Male patients with female partners are required and must agree to use 2 forms of contraception, one of which is a barrier method, throughout the study and for at least 28 days following the last dose of study drug.

Highly effective forms of contraception include:

- a. Abstinence

Abstinence is only acceptable as true abstinence (i.e., when this is in line with the preferred and usual lifestyle of the subject). Periodic abstinence (e.g., calendar, ovulation, symptothermal, post-ovulation methods), declaration of abstinence for the duration of a study, and withdrawal are not acceptable methods of contraception.

- b. Intrauterine device or intrauterine system
- c. Oral contraceptive plus a barrier method
- d. Diaphragm with vaginal spermicidal cream
- e. Vaginal spermicide with a condom
- f. Surgical sterilization (≥ 6 months postsurgery)

If a patient is usually not sexually active but becomes active, they, with their partner, must comply with the contraceptive requirements detailed above.

4.6.5 Sperm Donation:

Male patients must agree to not donate sperm during the study and for at least 28 days after the last dose of study drug.

